**Study Protocol**

**(Pages 2 – 5)**

**April 8, 2019**

## **Study Protocol**

Study titled “The Effectiveness of Game-Based Virtual Reality Approach in Patients with Subacromial Impingement Syndrome” was approved by Marmara University Faculty of Health Sciences Ethical Committee at the meeting on 29.11.2018 with approval number: 36 (Annex-1).

The legal representatives of the patients who participated in the study will be informed about the aim, duration and the programs to be applied throughout the study. Volunteer Information Form will be signed and approved in accordance with the standards deemed appropriate by the Ethical Committee of Marmara University Faculty of Health Sciences. The study will be conducted in accordance with the Declaration of Helsinki.

### **Hypothesis of the Study**

H0: Addition of game-based virtual reality exercises to the rehabilitation program in patients with subacromial impingement syndrome does not contribute positively in improving the effectiveness of upper extremity for pain, range of motion and disability

H1: Addition of game-based virtual reality exercises to the rehabilitation program in patients with subacromial impingement syndrome contribute positively in improving the effectiveness of upper extremity for pain, range of motion and disability.

### **Randomization of the Study Groups**

Individuals with Subacromial Impingement Syndrome applying to Cadde Medical Center for treatment will be invited to participate in the study. Individuals who volunteered to participate and whom met the criteria for participation will be randomized with simple random sampling method and will be divided into two groups. In both groups participants will receive conventional physiotherapy and rehabilitation. In the study group, 10 minutes of exercises with the game-based virtual reality exercises will added to the conventional physiotherapy and rehabilitation methods

### **Inclusion Criteria**

- Volunteered to participate in the study,
- Aged between 18-65 years

### Exclusion Criteria

- Any visual or hearing problem,
- Other neurological, orthopedic or rheumatic problems that may restrict shoulder motion or cause pain,
- Having a physical disability or uncontrolled chronic systemic disease,
- Major trauma,
- Treatment for shoulder problems within the last 6 months,
- History of epilepsy

### Evaluations

A Physiotherapist will applying the following evaluation parameters at the baseline, and at the end of 4-weeks treatment program, the same physiotherapist will be applying evaluation parameters. Primary outcome measures and applied evaluations are shown in Table 1.

**Table 1.** Primary outcome measures and evaluation methods

Primary Outcome Measures	Evaluation Methods
Range of Motion (ROM)	Goniometer
Pain	Visual Analogue Scale (VAS)
Disability	The Disabilities of the Arm, Shoulder and Hand (DASH) Questionnaire
Quality of Shoulder Function	Constant-Murley Score
Muscle Strength	Dynamometer
Pain Threshold	Algometer
Proprioception	Marmara Visual Auditory Joint Education Device (MarvaJED)
Kinesiophobia	Tampa Kinesiophobia Scale (TKS)
Satisfaction of the Treatment	Visual Analogue Scale (VAS)

The range of motion will be defined with ‘goniometer’, the pain with ‘Visual Analogue Scale (VAS)’, the disability with ‘The Disabilities of the Arm, Shoulder and Hand (DASH) Questionnaire’, the quality of shoulder function with ‘Constant- Murley Score’, the muscle strength with ‘dynamometer’, the pain threshold with algometer, the proprioception with

‘Marmara Visual Auditory Joint Education Device (MarvaJED)’, the kinesiophobia with ‘Tampa Kinesiophobia Scale (TKS), the satisfaction of the treatment with ‘Visual Analog Scale (VAS)’.

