**Statistical Analysis Plan (SAP)**

**(Pages 6 – 7)**

**April 8, 2019**

## **Statistical Analysis Plan (SAP)**

The statistical program Statistical Package for Social Sciences (SPSS) Version 11.5 (SPSS Inc., Chicago, IL, USA) will be used in the data analysis of the study. The p value of  $p < 0.05$  will be considered to be statistically significant in the data analysis. The initial demographic characteristics (age, boy, body weight) of all patients included in the study will be calculated.

‘Shapiro-Wilks Test’ will be used to investigate the appropriateness of the variables to normal distribution. ‘t-test’ will be used to compare the parameters of normal distribution in order to investigate the efficacy studies before and after the treatment; ‘Wilcoxon Test ‘ will be used to compare the parameters that do not comply with normal distribution.

**The Effectiveness of Game-Based Virtual Reality Approach in Patients with  
Subacromial Impingement Syndrome**

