**Do you have any additional problem?**

**No:**

**Yes/ If yes, What is it?**

**Assessment of Pain - Visual Analogue Scale**

- How severe is your shoulder pain during activity?

0.....5.....10  
(no pain) (worst possible pain)

- How severe is your shoulder pain during rest?

0.....5.....10  
(no pain) (worst possible pain)

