1. NO PAIN      2. MILD PAIN      3. MODERATE PAIN      4. SEVERE PAIN

A2. LEVEL OF PAIN

If 0 means no pain and 15 means the worst pain you can have, **please circle the number** which describes your shoulder pain when you are doing **normal** activities:

☺ 0 1 2 3 4 5 6 7 8 9 10 11 12 13 14 15 ☹

NONE      MILD      MODERATE      SEVERE      UNBEARABLE

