**E. Range of Motion**

Copy the movements the model is performing – it may be useful to perform this exercise in front of a mirror.

Starting from left to right in each row

- **Tick the box** (below each photograph) if you are **able to perform the action**
- **Leave the box blank** if you **cannot perform** the action

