**F. Strength**

Look at the two photographs below. Try to hold your arm in this position for 3 seconds each time carrying weights in the plastic bag.

Please use as weights within the plastic bag:

- **Bags of sugar**
- and/or
- **Filled plastic bottles of milk** (may be filled with water)
- and/or
- **Whatever is available for you with known weight**

Please record in the spaces below what was **the maximum weight** in kilograms (or pounds) or litres (or pints) that you **were able to hold in this position for 3 seconds** for each arm.

Seen from the front

seen from above

The maximum weight that I was able to hold in this position for 3 seconds:

Right Arm:		Kilograms/Litres	Left Arm:		Kilograms/Litres
Right Arm:		Pounds/Pints	Left Arm:		Pounds/Pints

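### Nine domains are labelled primary, the hypothesis names three, and no rule says which results make the trial positive or what the 5% level covers

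*Combined protocol and SAP*

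**What the plan says.** **Evaluations and Table 1.** "Primary outcome measures and applied evaluations are shown in Table 1". The table's heading calls all its entries primary. There are nine: range of motion, pain, disability, quality of shoulder function (Constant-Murley), muscle strength, pain threshold, proprioception, kinesiophobia and satisfaction. No outcome is called secondary.

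**Hypothesis of the Study.** H1 is that adding VR exercises will "contribute positively in improving the effectiveness of upper extremity for pain, range of motion and disability". That is three domains, joined by the word *and*, in a stated direction.

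**Statistical Analysis Plan.** A p value below 0.05 "will be considered to be statistically significant in the data analysis". A t-test is used for normally distributed variables, "in order to investigate the efficacy studies before and after the treatment", and a Wilcoxon test for the others. No between-group test and no sidedness are named. Nothing is said about several primary outcomes.

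**Annex 2.** The forms record more than one variable in several domains. Pain has two VAS items: one during activity, and one that asks "How severe is your shoulder pain during rest". Range of motion and muscle strength each cover ten movements on each side. Satisfaction has four scales.

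**The concern.** A reader of the plan cannot tell which result would count as showing that VR helps. Table 1 offers nine candidates and the hypothesis offers three. The SAP does not link either list to a decision.

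Four of the nine are clearly outside the hypothesis: muscle strength, proprioception, kinesiophobia and satisfaction. Nothing in the plan stops a single p<0.05 on one of these from being presented as a primary success for VR. Nor does the plan say what a mixed pattern on pain, motion and disability would mean for H1. A rule chosen once the results are known would not be credible, so it has to be written beforehand.

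**Working it through.** **1. The plan's own figure.** The only figure is p<0.05. The documents give no sample size, power, effect size or family-wise error rate, so there is nothing further to reproduce.

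**2. The two lists side by side.**

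| Table 1 domain | Relation to the hypothesis |
|---|---|
| Pain, range of motion, disability | Named |
| Constant-Murley, pain threshold | Not named, but overlapping in content |
| Muscle strength, proprioception, kinesiophobia, satisfaction | Outside |

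Constant-Murley is counted as overlapping because its form in Annex 2 has a pain item (the number "which describes your shoulder pain when you are doing" normal activities), a movement section ("Copy the movements the model is performing") and a strength section ("Try to hold your arm in this position for 3 seconds each time carrying weights in the plastic bag").

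**3. Illustration of the error rate.** Assumptions, none of them from the documents:
- one between-group test per domain, so k = 9;
- any one significant result counts as success;
- VR adds nothing on any outcome;
- the test statistics are normal with a common correlation ρ, varied from 0 to 0.9.

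For independent tests with false-positive probability a each, P(at least one) = 1 − (1 − a)^k.
- Two-sided 0.05, favouring VR: a = 0.025, so 1 − 0.975^9 = 0.204.
- Two-sided 0.05, either direction: a = 0.05, so 1 − 0.95^9 = 0.370.
- One-sided 0.05, favouring VR: a = 0.05, so again 0.370.

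For ρ > 0, in one direction, P = 1 − ∫ φ(u) Φ[(c − √ρ·u)/√(1 − ρ)]^k du. Here c = 1.96 for two-sided tests and 1.645 for one-sided tests. For either direction, the term raised to the power k is the probability of lying between −c and c.

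| Nine tests, at least one false result | ρ = 0 | 0.3 | 0.5 | 0.7 | 0.9 | One test |
|---|---|---|---|---|---|---|
| Two-sided 0.05, favouring VR | 20% | 17% | 13% | 10% | 6% | 2.5% |
| Two-sided 0.05, either direction | 37% | 33% | 27% | 20% | 12% | 5% |
| One-sided 0.05, favouring VR | 37% | 29% | 23% | 18% | 11% | 5% |

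**4. The three hypothesis domains alone**, uncorrected, with two-sided 0.05 tests and any one counting. Favouring VR: 1 − 0.975^3 = 7.3% at ρ = 0, falling to 4.2% at ρ = 0.9. Aligning Table 1 with the hypothesis removes most of the excess but not all of it, so a rule for the three is still needed.

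**5. Error after the change**, with no effect on any outcome. One primary outcome: 2.5% favouring VR, 5% either way. Holm over three: 2.5% to 1.5% favouring VR and 4.9% to 3.0% either way, for ρ from 0 to 0.9.

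**6. Power cost.** An outcome with 80% power at two-sided 0.05 has a mean test statistic of 1.960 + 0.842 = 2.802. The first Holm step uses 0.05/3, with critical value 2.394, so its power is Φ(2.802 − 2.394) = 66% if that outcome alone responds. Requiring all three to be significant, each with 80% power, gives 0.8^3 = 51% at ρ = 0, then 57%, 61%, 66% and 72% at ρ = 0.3, 0.5, 0.7 and 0.9.

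**The case against.** The strongest reply rests on the word *and* in H1. If pain, range of motion and disability must all be significant, the chance of a false claim does not inflate. That is right as statistics, but no section states such a rule, and a table of nine primary outcomes does not fit it. What stands is that the basic defect is the undefined success rule. Inflation is one possible consequence of it.

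A second reply is that the calculation describes an analysis the SAP does not contain, since its tests are tied to before and after treatment. This also stands, and it is why the figures are an illustration.

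A reader might draw stronger conclusions that the documents do not support:

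- *That the trial has a false-positive rate of 20% or 37%.* Those values need independent tests and a rule that any one result suffices. The outcomes overlap in content, so independence is unlikely. At the other end, 6% needs a correlation of 0.9 between every pair, for which the documents give no support either.
- *That independence gives a ceiling on the plan's error.* It does so only for exactly nine tests with non-negative correlations and a fixed sidedness. The forms hold more than nine variables, and sidedness is not stated.
- *That the SAP breaches the error level it promises.* It sets a significance threshold and claims no family-wise level. The fault is that it does not say what the 5% covers.
- *That satisfaction drops out of the count because it has no baseline.* A between-group comparison of post-treatment values needs none.

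**Conclusion.** The point holds, and it should be settled before data are seen. The mismatch between Table 1 and the hypothesis, and the lack of any lead outcome, order, adjustment or success rule, are plain from the text and rest on no assumption. As written, the plan does not define a positive trial and leaves room for a primary claim on any of four outcomes outside the hypothesis.

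The size is conditional. Under the two-sided illustration the chance of a false claim favouring VR is about 2.5 to 8 times that of a single test (6.2/2.5 and 20.4/2.5), and about 13% to 17% at correlations of 0.5 to 0.3. These are not bounds: selecting among the separate pain, motion, strength and satisfaction variables would add tests.

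**What to change.** Before data are seen, align Table 1 with the hypothesis by one of these routes. The sponsor chooses the route and the variables.

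- **(a)** Name one primary outcome from the hypothesis, for example DASH total at 4 weeks.
- **(b)** Name one variable for each of pain, range of motion and disability, and test the three with Holm at two-sided 0.05. This means choosing between the two pain VAS items and among the ten movements.

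A rule that all three named variables must be significant in favour of VR is a possible alternative. It needs no adjustment but costs more power.

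Under any route, state in the SAP that the 5% level applies to the between-group comparison at the end of the 4-week programme. Which model to use for that comparison is a separate point. Relabel the other Table 1 outcomes as secondary, reported with between-group estimates and 95% confidence intervals and no confirmatory claim.

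**Cost.** Wording in Table 1 and the SAP, and no new data. Fewer outcomes can support a primary claim. Route (a) costs the named outcome no power. Under route (b), an outcome with 80% power at 0.05 falls to about 66% at the first Holm step if it alone responds. Under the all-three rule, overall power is 51% to 72% when each outcome has 80%. The documents give no sample size, so the trial's actual power under any route cannot be computed.

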### **Treatment Program**

The participants in the study will be rehabilitated in Cadde Medical Center for 5 times a week for 4 weeks, a total of 20 sessions (Duration of one session is 60 minutes).

Group I (Control Group) will receive conventional physiotherapy and rehabilitation treatment program

Group II (Study Group) will receive conventional physiotherapy and rehabilitation treatment program and game-based virtual reality exercises (with a device named USE-IT) (10 minutes).

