### **Game-Based Virtual Reality Exercises**

In addition to the conventional physiotherapy and rehabilitation program, a 10-minute game-based virtual reality exercises will be applied. A game-based virtual reality device named USE-IT will be added to the rehabilitation program. USE-IT is a technological rehabilitation system designed by the Department of Physiotherapy and Rehabilitation at Hacettepe University (Ankara, Turkey). It is a smart gaming device which has been used in patients who suffer from movement loss in their upper extremities due to various neurological and orthopedic reasons.

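### Does one 60-minute session length for everyone contradict adding 10 minutes of virtual reality to a common programme?

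*Combined protocol and SAP*

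**What the plan says.** The Treatment Program section opens with a statement about everyone, "The participants in the study will be rehabilitated in Cadde Medical Center", and goes on to the schedule: "5 times a week for 4 weeks, a total of 20 sessions (Duration of one session is 60 minutes". No other session length appears, and none is given by group. The same section then lists what each group receives. For controls, "Group I (Control Group) will receive conventional physiotherapy and rehabilitation treatment program". The study group receives that programme "and game-based virtual reality exercises (with a device named USE-IT) (10 minutes" in brackets.

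Three other sections describe how VR relates to the conventional programme:

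- Randomization of the Study Groups: "In both groups participants will receive conventional physiotherapy and rehabilitation", and for the study group "10 minutes of exercises with the game-based virtual reality exercises will added to the conventional physiotherapy and rehabilitation methods".
- Game-Based Virtual Reality Exercises: "In addition to the conventional physiotherapy and rehabilitation program, a 10-minute game-based virtual reality exercises will be applied".
- Hypothesis of the Study: H1 concerns "Addition of game-based virtual reality exercises to the rehabilitation program".

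The section on the conventional programme lists nine components, from TENS to capsule stretching, with no minutes, sets or repetitions. The SAP does not mention treatment time.

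**The concern.** If every session lasts 60 minutes in both groups and conventional therapy fills the control session, then 10 minutes of VR can enter a study-group session only by displacing conventional therapy. The contrast would then be VR in place of part of the usual treatment, while H1 asks about VR on top of it. If instead VR follows a full 60-minute session, the stated length is wrong for the study group. That group also gets more supervised treatment, so a benefit could come from the extra time and not from VR as such.

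At stake is the meaning of the between-group difference. A reader who cannot tell which comparison was made cannot say what the result supports.

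**Working it through.** **Inputs, all from the protocol.** 5 sessions a week, 4 weeks, 20 sessions and 60 minutes per session (Treatment Program); 10 minutes of VR for the study group (Treatment Program, Randomization of the Study Groups, Game-Based Virtual Reality Exercises). Conventional minutes per session, *c*, are not stated.

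**Assumption.** VR is given at each of the 20 sessions. The protocol says 10 minutes without saying per session, but this is the natural reading.

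**Step 1. The plan's own figure.** 5 × 4 = 20 sessions, which reproduces exactly. VR total: 20 × 10 = 200 minutes.

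**Step 2. When do the statements conflict?** With the same conventional content in both groups, a study-group session needs *c* + 10 minutes. This fits in 60 when *c* ≤ 50. The values of *c* below are illustrative.

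| *c* (minutes) | *c* + 10 | Fits in 60? | Control time not filled by conventional content (60 − *c*) |
|---|---|---|---|
| 40 | 50 | yes | 20 |
| 50 | 60 | yes | 10 |
| 55 | 65 | no | 5 |
| 60 | 70 | no | 0 |

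A contradiction therefore needs *c* > 50, and the documents do not say so.

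**Step 3. Treatment time under each reading.**

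- *A: 60 minutes is the conventional session and VR comes on top.* Study 20 × 70 = 1400 minutes; control 20 × 60 = 1200. Conventional time is 1200 in both. Difference in total: 200/1200 = 16.7% more in the study group.
- *B: 60 minutes is a cap in both groups and conventional therapy fills it in controls.* Total 1200 each. Conventional time is 20 × 50 = 1000 in the study group against 1200 in controls, or −200/1200 = −16.7%.
- *C: 60 minutes is a slot and the common content takes 50 minutes or less.* Conventional time is equal. With *c* = 50, active treatment is 1200 against 20 × 50 = 1000 minutes (200/1000 = 20% more). With *c* = 40 it is 20 × 50 = 1000 against 20 × 40 = 800 (200/800 = 25% more).

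**Step 4. Which readings test H1?** Under A and C both groups get the same conventional programme and only one gets VR, which is H1's add-on contrast. Only B departs from H1. B requires conventional treatment to be shortened in the study group, and no section says that. The hypothesis, the randomization section, the group descriptions and the VR section all say the opposite.

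**The case for a change.** The strongest case for acting runs as follows. The conventional programme is the only treatment named for a control session, so the plain reading is that it occupies the 60 minutes; the same programme plus 10 is then 70. Reading C avoids this only by leaving at least 10 minutes of each control session with no listed treatment, which no section mentions. No reading equalises both conventional dose and active time. The participant tracking form in Annex 2 has no field for session minutes, so the delivered contrast could not be recovered from it. Satisfaction with treatment is among the primary outcomes, and its form asks about the physiotherapist, which extra contact could plausibly influence.

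Part of this stands. The protocol does not say whether the 60 minutes include VR, and under A or C any effect of VR comes together with 200 more minutes of treatment.

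It does not amount to a fault in the plan. One bracketed session length cannot outweigh several consistent descriptions of VR as an addition, and it can equally describe the base session or the booked slot. Separating VR from the time it takes is a different question from H1, and would need a time-matched control. An add-on comparison is a legitimate choice, and it answers whether adding these exercises helps. A conclusion worded as the effect of adding 10 minutes of VR exercise would largely repeat H1 and the randomization section. A warning against a broader claim is aimed at a conclusion that neither document draws.

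**Conclusion.** No change to the plan follows. The session length and the added VR are compatible unless the conventional programme exceeds 50 minutes, and its duration is not given. The stated intent is addition throughout. Followed as written, the trial gives both groups the conventional programme and one group VR as well, and so tests H1.

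What remains is a gap in description: session length and conventional time by group. It is worth 200 minutes over the course, either as additional treatment in the study group (16.7% on reading A; 20% on reading C with 50 minutes of conventional content) or, on reading B, as 16.7% less conventional time. These figures assume VR at all 20 sessions; those for B and C also assume how the 60 minutes are filled. The treating centre knows how sessions were run, and the trial report would ordinarily state it. Writing the minutes down would help readers but would correct no wrong rule, test or result. No view is taken here on which duration is intended.

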### **Game-Based Virtual Reality Exercises**

In addition to the conventional physiotherapy and rehabilitation program, a 10-minute game-based virtual reality exercises will be applied. A game-based virtual reality device named USE-IT will be added to the rehabilitation program. USE-IT is a technological rehabilitation system designed by the Department of Physiotherapy and Rehabilitation at Hacettepe University (Ankara, Turkey). It is a smart gaming device which has been used in patients who suffer from movement loss in their upper extremities due to various neurological and orthopedic reasons.

